9.3. Statistical Analyses

The SAP will be developed and finalized before analyses are performed and will describe the analyses and procedures for accounting for missing, unused, and spurious data. This section is a summary of the planned statistical analyses of the primary and secondary endpoints.

9.3.1. General Considerations

Baseline demographic and other characteristics will be tabulated for the FAS and summarized by treatment group. Quantitative variables will be described by standard descriptive statistics and qualitative variables will be summarized by frequency tables with number and proportion in each category.

For continuous endpoints, an MMRM or ANCOVA model will be used to analyze change from baseline, whichever is appropriate. Estimated mean differences between treatments groups will be calculated.

For categorical endpoints, proportion of participants for each category will be summarized for each group.

For count endpoints, the total number of the events and average number of events will be summarized for each group.

Time to event will be summarized graphically using Kaplan-Meier plots for each treatment group. Treatment comparisons will be conducted using log-rank test or Cox proportional hazard model as appropriate.

9.3.2. Primary Endpoint(s)/Estimand(s) Analysis

9.3.2.1. Definition of Endpoint(s)

The primary efficacy endpoint is the change in viral SARS-CoV-2 RNA level from baseline to Day 5 as measured in NP swabs.

9.3.2.2. Main Analytical Approach

The primary analysis for mean change in SARS-CoV-2 RNA level from baseline will be performed using a MMRM. The analysis will include the fixed effects of treatment, geographic region, baseline viral RNA level, visit, and treatment-by-visit interaction. An unstructured (co)variance structure will be used to model the within-participant variability. The LS means and treatment difference for each visit will be calculated and presented with their corresponding 95% CIs. The primary comparison for treatment effect will be the difference in LS means and 95% CI at Day 5. The primary analysis will be performed using mITT analysis set.

The secondary analysis for primary endpoint will be performed using the mITT1 analysis set.

9.3.3. Secondary Endpoints

9.3.3.1. Time to 2 consecutive negative rapid antigen test results obtained at least 24(-2)h apart through Day 28

For the event of 2 consecutive negative rapid antigen test results obtained at least 24(-2)h apart through Day 28, the date of the first negative rapid antigen test result will be considered the First Event Date.

Time to 2 consecutive negative rapid antigen test results obtained at least 24(-2)h apart for the purpose of this study is defined as:

- For a participant achieving the event, time to event will be calculated as (First Event Date) – (First Dose Date) +1.
- For a participant not achieving the event (censored), censoring date will be at the last date of rapid antigen test measurement, and time will be calculated as (Censoring Date) – (First Dose Date) +1 or Day 27 whichever occurs first (Day 27 is the last

possible day to achieve 2 consecutive negative rapid antigen test results obtained at least 24(-2)h apart through Day 28).

Cox proportional hazard model analyses will be used for time to 2 consecutive negative rapid antigen test results obtained at least 24(-2)h apart in mITT analysis set. Cox proportional hazard model will include treatment, geographic region and potential covariates as appropriate. The treatment group comparison will be presented as the estimate of the hazard ratio, 95% CI and p-value. In addition, time to 2 consecutive negative rapid antigen test results obtained at least 24(-2)h apart will be summarized graphically using Kaplan-Meier plots for each of the treatment groups in mITT analysis set.

Similar analyses for time to 2 consecutive negative rapid antigen test results obtained at least 24(-2)h apart will also be performed in the mITT1 analysis set.

9.3.3.2. Time (days) to sustained alleviation of all targeted signs and symptoms through Day 28

Sustained alleviation of all targeted COVID-19 signs/symptoms is defined as the event occurring on the first of 2 consecutive days when all symptoms scored as moderate or severe at study entry are scored as mild or absent AND all symptoms scored mild or absent at study entry are scored as absent. The first day of the 2 consecutive-day period will be considered the First Event Date.

For symptoms with no reported severity in baseline, the symptom will have to be absent in order to be counted as sustained alleviated (missing severity at baseline will be treated as mild).

Day 27 is the last possible day that symptom alleviation can be achieved (definition includes data from the subsequent day) and Day 28 is the last day participants report their daily signs and symptoms.

The time to sustained symptom alleviation for the purpose of this study is defined as:

- For a participant with sustained symptom alleviation, time to event will be calculated as (First Event Date) – (First Dose Date) +1.
- For a participant that either completes Day 28 of the study or discontinues from the study before Day 28 without sustained symptom alleviation(censored), censoring date will be at the last date on which symptom alleviation is assessed, and time will be calculated as (Censoring Date) – (First Dose Date) +1 or Day 27 whichever occurs first.

Participants who are hospitalized for the treatment of COVID-19 or die from any cause during the 28-day period will be classified as not achieving sustained symptom alleviation and will be censored at day 27.

Cox proportional hazard model analyses will be used for time to sustained symptom alleviation in mITT analysis set. Cox proportional hazard model will include treatment, geographic region and potential covariates as appropriate. The treatment group comparison

will be presented as the estimate of the hazard ratio, 95% CI and p-value. In addition, time to sustained symptom alleviation will be summarized graphically using Kaplan-Meier plots for each of the treatment groups in mITT analysis set.

Similar analyses for time to sustained symptom alleviation will also be performed in the mITT1 analysis set.

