6.2. Secondary Endpoint(s)

6.2.1. Time to 2 Consecutive Negative Rapid Antigen Test Results Obtained at least 24(-2)h Apart through Day 28

The event of 2 consecutive negative rapid antigen test results obtained at least 24(-2)h apart through Day 28 is defined as achieving two consecutive non-missing rapid antigen test with negative results through Day 28, where the two tests are at least 22 hours and at most 7 days apart. For the event of 2 consecutive negative rapid antigen test results obtained at least 24(-2)h apart through Day 28, the date of the first negative rapid antigen test result will be considered the First Event Date.

Time to 2 consecutive negative rapid antigen test results obtained at least 24(-2)h apart for the purpose of this study is defined as:

- For a participant achieving the event, time to event will be calculated as (First Event Date) – (First Dose Date) +1.
- For a participant not achieving the event (censored), censoring date will be at the last date of rapid antigen test measurement, and time will be calculated as (Censoring Date) – (First Dose Date) +1 or Day 27 whichever occurs first (Day 27 is the last possible day to achieve 2 consecutive negative rapid antigen test results obtained at least 24(-2)h apart through Day 28).

Participants who are hospitalized for the treatment of COVID-19 or die from any cause during the 28-day period will be classified as not achieving the event and will be censored at Day 27.

Cox proportional hazard model analyses will be used for time to 2 consecutive negative rapid antigen test results obtained at least 24(-2)h apart in mITT analysis set. Cox proportional hazard model will include treatment, geographic region, baseline viral load (< 4 or ≥ 4) and time since the last vaccination (≤ 6 months, > 6 months or unvaccinated) as appropriate. The treatment group comparison will be presented as the estimate of the hazard ratio, 95% CI and p-value. In addition, time to 2 consecutive negative rapid antigen test results obtained at least 24(-2)h apart will be summarized graphically using Kaplan-Meier plots for each of the treatment groups in mITT analysis set.

The log-rank test will be performed as additional analysis to compare the treatment group using mITT analysis set.

Similar analyses for time to 2 consecutive negative rapid antigen test results obtained at least 24(-2)h apart will also be performed in the mITT1 analysis set.

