6.2.2. Time (days) to Sustained Alleviation of All Targeted Signs and Symptoms through Day 28

Sustained alleviation of all targeted COVID-19 signs/symptoms is defined as the event occurring on the first of 2 consecutive days when all symptoms scored as moderate or severe at study entry are scored as mild or absent AND all symptoms scored mild or absent at study entry are scored as absent. The first day of the 2 consecutive-day period will be considered the First Event Date.

For symptoms with no reported severity in baseline, the symptom will have to be absent in order to be counted as sustained alleviated (missing severity at baseline will be treated as mild).

Day 27 is the last possible day that symptom alleviation can be achieved (definition includes data from the subsequent day) and Day 28 is the last day participants report their daily signs and symptoms.

The time to sustained symptom alleviation for the purpose of this study is defined as:

- For a participant with sustained symptom alleviation, time to event will be calculated as (First Event Date) – (First Dose Date) +1.
- For a participant that either completes Day 28 of the study or discontinues from the study before Day 28 without sustained symptom alleviation(censored), censoring date will be at the last date on which symptom alleviation is assessed, and time will be calculated as (Censoring Date) – (First Dose Date) +1 or Day 27 whichever occurs first.

Participants who are hospitalized for the treatment of COVID-19 or die from any cause during the 28-day period will be classified as not achieving sustained symptom alleviation and will be censored at Day 27.

Cox proportional hazard model analyses will be used for time to sustained symptom alleviation in mITT analysis set. Cox proportional hazard model will include treatment, geographic region baseline viral load (< 4 or \geq 4) and time since the last vaccination (\leq 6 months, $>$ 6 months or unvaccinated) as appropriate. The treatment group comparison will be presented as the estimate of the hazard ratio, 95% CI and p-value. In addition, time to sustained symptom alleviation will be summarized graphically using Kaplan-Meier plots for each of the treatment groups in mITT analysis set.

Similar analyses for time to sustained symptom alleviation will also be performed in the mITT1 analysis set.

6.2.3. Incidence of Treatment Emergent Adverse Events (TEAEs); Incidence of SAEs and AEs Leading to Discontinuation

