Sustained is defined as NP swab SARS-CoV-2 RNA level not $\geq 2.0 \log_{10}$ copies/mL at any study visit (through Day 34) following the first study visit where the participant's NP swab SARS-CoV-2 RNA $<$ LLOQ.

Let t represent the study day t between Day 5 and 28 visit inclusive for which there is a measurement of SARS-CoV-2 RNA level.

Then a sustained event will correspond to the first possible value of t to satisfy the following criteria:

- a) The Day t SARS-CoV-2 RNA level is $<$ LLOQ
- b) At least one SARS-CoV-2 RNA measurement is $<$ LLOQ after Day t
- c) All available (non-missing) SARS-CoV-2 RNA measurements between Day t and Day 34 visit are $<$ LLOQ
- d) No more than 50% missingness between Day t and Day 34 are missing.

There are limitations to the timing of the first event date as NP viral RNA is generally only captured at scheduled visits during the study.

The Day 28 visit is the last possible day the sustained NP swab SARS-CoV-2 RNA $<$ LLOQ can be achieved.

The time to the sustained event is defined as:

- For a participant with sustained event at Day t , the First Event Date is the date of the Day t measurement, and time to event will be calculated as (First Event Date) – (First Dose Date) +1.
- For a participant for which no possible value of $t \leq$ the Day 28 visit satisfies the criteria for a sustained event (censored), censoring date will be the date of the last available protocol-specified SARS-CoV-2 RNA measurement other than Day 34 visit, and time will be calculated as (Censoring Date) – (First Dose Date) +1.

6.3.6. Rebound in SARS-CoV-2 RNA Level in NP Swabs at Follow-up ie, Any Study Visit from Day 10 to through Day 34, Defined as a Half (0.5) Log₁₀ Copies/mL Increase or Greater in SARS-CoV-2 RNA Level Relative to SARS-CoV-2 RNA Level on Day 5 and with a Follow-up Viral RNA Level ≥ 2.5 Log₁₀ Copies/mL

The number and proportion of participants with rebound in SARS-CoV-2 RNA level in NP swabs up at follow-up will be summarized by treatment group. The analyses will be done using mITT analysis set.

In addition, two alternative definitions of rebound will also be evaluated:

- Rebound that is defined as: SARS-CoV-2 RNA level in NP swabs at follow up (ie, any study visit after Day 5 through Day 34) that is defined as a half (0.5) log₁₀ copies/mL increase or greater in SARS-CoV-2 RNA level relative to SARS-CoV-2 RNA level on Day 5, with a follow-up viral RNA level ≥ 3.0 log₁₀ copies/mL.

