6.3.8. Change from Baseline in SARS-CoV-2 Viral RNA Level in Plasma, Over Time

Change from baseline in SARS-CoV-2 viral RNA level in plasma, over time will be analyzed similar to the primary endpoint using MMRM model in mITT analysis set. The LS means and treatment difference for each visit will be calculated and presented with their corresponding 95% CIs.

6.3.9. Proportion of Participants with COVID-19-related Hospitalization >24h or Death from Any Cause through Day 28

The number and proportion of participants with COVID-19-related hospitalization >24h or death from any cause through Day 28 will be summarized by treatment group. The analyses will be done using the mITT analysis set.

6.3.10. Number of COVID-19-related Medical Visits through Day 34

Number of COVID-19-related medical visits through Day 34 will be summarized by treatment group descriptively (n, mean, standard deviation, median, min, max). The analysis will be done using the mITT analysis set.

6.3.11. Time (days) to Sustained Resolution of All Targeted Signs and Symptoms through Day 28

Sustained resolution of all targeted COVID-19 signs/symptoms is defined as the event occurring on the first of 2 consecutive days when all targeted COVID-19 symptoms are scored as absent. The first day of the 2 consecutive-day period will be considered the First Event Date.

For symptoms with no reported severity in baseline, the symptom will have to be absent in order to be counted as sustained resolution (missing severity at baseline will be treated as mild).

Day 27 is the last possible day that symptom resolution can be achieved (definition includes data from the subsequent day) and Day 28 is the last day participants report their daily signs and symptoms.

The time to sustained symptom resolution for the purpose of this study is defined as:

- For a participant with sustained symptom resolution, time to event will be calculated as (First Event Date) – (First Dose Date) +1.
- For a participant that either completes Day 28 of the study or discontinues from the study before Day 28 without sustained symptom resolution (censored), censoring date will be at the last date on which symptom resolution is assessed, and time will be calculated as (Censoring Date) – (First Dose Date) +1 or Day 27 whichever occurs first.

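### Participants whose data stop early are censored at an observation that could never have been confirmed as an event, which lowers hazards and event curves: negligible for the two tested endpoints, visible for exploratory swab clearance

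*Protocol*

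**What the plan says.** **Event dates.** For sustained alleviation (Protocol 9.3.3.2, SAP 6.2.2), "The first day of the 2 consecutive-day period will be considered the First Event Date". For the antigen endpoint (Protocol 9.3.3.1, SAP 6.2.1), "the date of the first negative rapid antigen test result will be considered the First Event Date", and SAP 6.2.1 requires the second negative test 22 hours to 7 days later. For swab clearance (SAP 6.3.5), criterion (b) requires at least one later swab below the LLOQ. Criterion (d) allows at most half the measurements from Day t to Day 34 to be missing.

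**Censoring dates for participants without an event.**

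- Symptom alleviation: "censoring date will be at the last date on which symptom alleviation is assessed", capped at Day 27. The rule covers completers and dropouts alike: "For a participant that either completes Day 28 of the study or discontinues from the study before Day 28".
- Antigen: "censoring date will be at the last date of rapid antigen test measurement", capped at Day 27.
- Swab clearance: "censoring date will be the date of the last available protocol-specified SARS-CoV-2 RNA measurement other than Day 34 visit".
- Symptom resolution (SAP 6.3.11): "censoring date will be at the last date on which symptom resolution is assessed", capped at Day 27.

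**Where the plan already steps back.** SAP 6.2.2 gives the reason for its cap: "Day 27 is the last possible day that symptom alleviation can be achieved (definition includes data from the subsequent day"). SAP 6.3.5 leaves the Day 34 swab out of the censoring date and names the Day 28 visit as the last possible event. Both adjustments apply only at the end of scheduled follow-up.

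**The concern.** Take a participant whose last diary entry is on Day k, before Day 28. An event on Day k would need an entry on Day k+1, which does not exist, so the last day on which an event could be recorded is k-1. Censored at k, the participant sits in the Day k risk set with no chance of an event. Someone who first meets the alleviation criterion on Day k and then stops the diary is counted that day as at risk without an event.

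For swabs the impossible stretch is at least one visit interval of 5 to 7 days, and criterion (d) can lengthen it. A participant who completes the study but misses only the Day 34 swab is also affected, because the Day 28 result can no longer be confirmed.

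At stake are the Kaplan-Meier curves for all four endpoints. If dropout differs between arms, the hazard ratios are affected too, including the two in the Hochberg step.

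**Working it through.** **The plan's own figures.** The documents state no event count, power or dropout rate for these endpoints. The nearest figure is the 15% non-evaluable rate for the primary endpoint. That sample size reproduces, 315/(0.90 × 0.85) = 411.8 against 411, but does not bear on this point. All dropout rates, medians and hazard ratios below are assumptions, and dropout is taken as unrelated to outcome.

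**Daily endpoints, hazard within an arm.** On day t, those whose last entry is day t count as at risk but cannot have an event. The fitted hazard is therefore the true hazard times

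1 − (share stopping on day t) / (share still providing data on day t).

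- 15% dropout spread evenly over Days 1 to 27. Day 1: 1 − 0.00556/1 = 0.994. Day 27: 1 − 0.00556/(1 − 0.15 × 26/27) = 0.994 (0.9935).
- 5% dropout spread evenly: 0.998.
- 15% dropout all in Days 1 to 7. Day 7: 1 − 0.02143/(1 − 0.15 × 6/7) = 0.975. At 10% the minimum is 0.984, and at 5% it is 0.993.

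Censoring one day earlier removes the second term, and the ratio is 1.000 on every day.

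**Daily endpoints, hazard ratio.** Cox model with Efron ties, 370 participants (411 × 0.9), 2:1, median 7 days, true HR 1.3, 400 simulated trials per row:

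| Dropout placebo / active | Pattern | HR as written | HR corrected |
|---|---|---|---|
| 15% / 15% | even | 1.297 | 1.297 |
| 15% / 15% | Days 1–7 | 1.300 | 1.300 |
| 20% / 5% | even | 1.310 | 1.302 |
| 20% / 5% | Days 1–7 | 1.316 | 1.297 |
| 5% / 20% | even | 1.289 | 1.297 |
| 5% / 20% | Days 1–7 | 1.281 | 1.300 |

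The SD of log HR is 0.11 to 0.13. The shifts for 20% against 5% are ln(1.3098/1.3015) = 0.006 and ln(1.3164/1.2966) = 0.015 on the log scale, or about 0.06 and 0.12 of that SD.

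**Swab clearance.** Visits are on Days 5, 10, 15, 21, 28 and 34. Assume a 10-day median and 6% dropout per visit. The true hazard at each of Days 5, 10 and 15 is 1 − 0.5^0.5 = 29.3%, so the true Day 15 curve is 1 − 0.7071³ = 64.6%.

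Suppose first that Day t counts in the denominator of criterion (d). A Day 5 event then needs swabs through Day 15, and Day 10 and Day 15 events need swabs through Day 21.

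- Day 5: 0.94² × 0.2929 = 0.259.
- Day 10: events 0.94² × 0.2071 = 0.183. At risk 0.06 + 0.94 × 0.7071 = 0.725, because people last swabbed on Day 10 stay in even if already clear on Day 5. Hazard 0.253.
- Day 15: events 0.94 × 0.1464 = 0.138. At risk 0.06 × 0.7071 + 0.94 × 0.5 = 0.512. Hazard 0.269.
- Curve: 1 − 0.741 × 0.747 × 0.731 = 59.5%.

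If Day t does not count, Day 5 and Day 10 events need swabs through Day 21, and a Day 15 event needs swabs through Day 28. The hazards are 0.243, 0.247 and 0.244, and the curve is 1 − 0.757 × 0.753 × 0.756 = 56.9%. With 0.97 in place of 0.94 (3% per visit), the two curves are 62.1% and 60.8%.

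Stepping back only to the last swab that has a later swab gives about 63% or 61% at 6% dropout, still low. Someone last swabbed on Day 10, for example, has 4 of 6 visits from Day 5 missing, so Day 5 cannot be an event either. Censoring at the last visit able to meet both (b) and (d) leaves only people who can have an event in each risk set and returns 64.6%.

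**The case against.** **The tested estimands are hazard ratios, not hazards.** This stands. With equal dropout the ratio does not move, and a fourfold imbalance moves it by a small fraction of its standard error. Nothing in the documents suggests such an imbalance.

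**The larger effect is on an exploratory endpoint.** This also stands. Swab clearance has no estimand and lies outside the multiplicity procedure.

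**The symptom wording may already mean the right date.** The last date on which alleviation is assessed could be the last day on which the two-day status could be evaluated, which is k-1. This is possible. The natural reading is the last diary day, since otherwise the added Day 27 cap would do nothing, but the cap could simply restate the preceding sentence. The antigen and swab rules name the last test and the last measurement, so they leave no such room. Either way, two programmers could derive different symptom dates.

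**A diary entry missed mid-study has the same effect.** This is true: the previous day cannot be confirmed while the person stays at risk. Correcting the censoring date does not address interior gaps.

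A reader might infer that the tested hazard ratios are materially biased, or biased in favour of nirmatrelvir/ritonavir. The documents support neither. The shift is small and its direction depends on which arm loses more people.

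**Conclusion.** The point holds. SAP 6.2.1 and 6.3.5 (with Protocol 9.3.3.1), and on the natural reading SAP 6.2.2 and 6.3.11 (with Protocol 9.3.3.2), keep early stoppers at risk when no event is possible. This lowers hazards and Kaplan-Meier event curves in each arm that loses participants. The plan accepts the principle at the end of follow-up but does not carry it to earlier last observations.

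For the two Hochberg-tested endpoints the effect is very small and does not threaten their interpretation. Daily hazards are 0.2% to 0.6% low with dropout spread out, and up to 2.5% low on a single day with 15% early dropout. For swab clearance the Day 15 curve is about 5 to 8 points low at 6% dropout per visit, and 2.5 to 4 points low at 3%. These sizes rest on the assumed dropout rates and medians and on dropout unrelated to outcome.

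Participants hospitalised for COVID-19 or who die are handled by a separate rule (censored at Day 27) where the plan applies it, and are not part of this point.

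**What to change.** Before unblinding, state in Protocol 9.3.3 and in SAP 6.2.1, 6.2.2, 6.3.5 and 6.3.11 that participants without an event are censored at the last date on which an event could still have been confirmed:

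- **Symptoms (alleviation and resolution):** the last diary day with a next-day entry. Say explicitly that this is what assessed means.
- **Antigen:** the last test followed by another test 22 hours to 7 days later.
- **Swabs:** the last visit up to Day 28 at which criteria (b) and (d) could both still be met given the swabs available. State whether Day t counts in the denominator of (d).

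Keep the Day 27 and Day 28-visit caps. The cost is one sentence per endpoint and a small derivation change, with no new data. Participants with no confirmable assessment contribute no risk time, and the number of them should be reported by arm.
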